**C.4. Intervention Arms (Table 4).**

**HVP curriculum.** Our HVP partners are two of 400 nationwide *Healthy Families America* (HFA) sites/chapters, housed at Antelope Valley Partners for Health and the Antelope Valley Children’s Bureau. The HFA model meets the DHHS criteria for an “evidence-based early childhood home visiting service delivery model” (See <http://homvee.acf.hhs.gov>). HFA services begin prenatally and continue until children are 2-5yo depending on the HVP model. The curriculum focuses on strengthening parent-child relationships and family functioning, promoting positive child development, and linkage to community resources (e.g., medical providers, financial/housing assistance, childcare, substance abuse treatment, community programs).

**HFA accredited home visitors** (Nurses) are matched to families on cultural background and language (English or Spanish), to provide culturally sensitive services. Home visitors are selected because of their personal characteristics (e.g., non-judgmental, compassionate, ability to establish a trusting relationship), their experience working with culturally diverse communities, and their skills to do the job. HFA home visitors are expertly trained and experienced in handling situations encountered while working with at-risk families. They receive training in cultural competency, substance abuse, reporting child abuse, domestic violence, and linkage to services in their community. Home visiting staff also receive intensive training specific to their role (e.g., identifying at-risk families, standardized assessments, phlebotomy, mental health referrals, promoting preventive health care, utilizing creative outreach efforts, establishing and maintaining trust with families, building upon family strengths, developing individual family support plans, teaching parent-child interaction, managing crises). Staff also receive weekly supervision, ongoing developmental training, and have limited caseloads (10-15 families) to meet their families’ needs.

**COPE** is a culturally sensitive, language specific, and community-forming model of implementation to deliver key nutrition, activity and feeding practice components as part of HVP services in a way that is engaging for families. COPE key components are summarized in **Table 4**, and outlined in detail below. Although mothers/infants are the focus of HVPs and COPE, visits are delivered in the home and, as is standard practice with HVPs, will engage other household members if possible (e.g., spouse).

**1. Maternal nutrition.** Home visitors teach mothers to prepare and store foods they receive from *WIC* and the *Food Bank*, and to gradually build healthier nutrition and activity goals congruent to their cultural practices and ethnic specific food palate: (a) increasing intake of vegetables and fruits (≥5 servings/day of fruits and vegetables) and integrating nutrient-dense ingredients in their families’ meals/recipes; (b) limiting intake of high-saturated fat and sugar in modifying families’ favorite recipes (the material is adapted to families’ cultural and personal preferences); (c) eliminating sugar-sweetened beverage intake, supported by the provision of information and activities on sugar content, long-term effects of high sugar consumption, importance of drinking water, and impact of advertising; (d) teaching healthy portion sizes using different visual activities. **2. Infants/young children nutrition.** The curriculum promotes sustained breastfeeding for the first two years and the gradual integration of complementary feeding (pureed and age-appropriate solid foods) that support healthy eating for infants. Mothers learn about feeding/eating developmental stages and transitions, and healthy feeding practices to promote: (a) responsiveness to child hunger and fullness cues; (b) the consumption of nutrient-dense foods (as opposed to energy-dense); (d) the transition to structured schedule for meals/snacks from complementary feeding; and (d) the use of non-food related child soothing techniques. Mothers also learn strategies to address neophobia, such as repeated multi-sensory (i.e., smell, touch, taste) exposures to nutrient-dense novel foods, gradual texture shaping, parents/caregivers modeling, and involvement of children in food selection and preparation; and strategies to handle meal-related tantrums (e.g., redirection, positive reinforcement of appropriate behaviors). **3. Maternal/child physical activity.** Although there is no unequivocally accepted guidelines for the number of minutes children 0-2yo should be active each day, the DHHS has summarized recommendations from the National Association for Sport and Physical Education, the American College of Sports Medicine, and the National Institutes of Health: (a) daily planned physical activities, including tummy time, that safely support the infant’s developmental milestones (e.g. head and neck self-support, rolling, floor sitting, kicking, crawling, reaching and grasping for objects, etc.); (b) engage in 30

	HVP	COPE
Maternal/infant health	x	
Child physical and social development	x	
Crime and domestic violence	x	
Child abuse and neglect	x	
Family economic stability	x	
Breastfeeding	x	x
Maternal nutrition		x
Physical activity and play		x
Infant nutrition/feeding practices		x

minutes of supervised but *unstructured* physical activity each day; and (c) avoid being sedentary for more than 60 minutes at a time, except when sleeping. The American Academy of Pediatrics (A.A.P.) Expert Committee further suggests limiting screen time. COPE is premised on the above guidelines in addition to CDC guidelines for adults (150 minutes of moderate intensity physical activity/week). COPE teaches parents to make activity/play a daily habit for their entire family by exploiting lifestyle activities (e.g., taking the stairs, walking to the shop). Home visitors help parents design activities around their local environment, schedule, and preferences, and to optimize their use of safe spaces. Parents are provided with information about resources and free group activities conducive to physical activity (e.g., parks, walking clubs, outings, etc.), and classes they can take with their children and with other HVP families. The curriculum emphasizes the importance of parents co-engaging in activities with their children to set a good example through modeling and to provide opportunities for their children to be physically active.

**COPE delivery format.** Our formative work and pilot research indicates that didactic and experiential approaches are needed to help families adopt behaviors that will promote their child’s health.

1. **Didactic education** focuses on in-home individualized coaching to help mothers implement changes in their “natural environment”. A strong emphasis is placed on *gradual goal setting* in which mothers set objectives for their own and/or their children’s weekly activity and diet (e.g., decreasing by “x” the number of sugar-sweetened beverages) and on *parent modeling* healthy behaviors (i.e., co-engaging in healthy behaviors with their children). Parents are taught *behavior management and cognitive-behavioral strategies* to change cues in their home environment. Mothers receive individual coaching to gradually eliminate high-energy dense foods from the home environment, and to modify the home to make it more conducive to exercising (e.g., removing computer/televisions from sleeping areas).

2. **Social experiential activities (Table 5)** were selected in response to: our theoretical framework that emphasizes social network influences; our pilot work that highlights existing social network barriers to behavior change; and families’ desire to learn through hands-on, social activities. These activities are already built into the service infrastructure at Antelope Valley Partners for Health, are integrated across all key content areas of COPE, and will be promoted to participants in the intervention arm (but not to participants in the control arm) by their home visitor. Participation by study participants will be monitored and recorded by activity staff. One central purpose of the communal activities is to foster new, yet sustainable social and community connections that will provide increased healthy behavior role models and social support for mothers. This will be achieved through activities that provide a context for repeated social connection among consistent groups of COPE participants in their neighborhoods, and through activities designed to foster group learning, discussion, and shared experiences that are aligned with the individual didactic learning in home. These social activities are similar to those delivered as part of the *National Institute of Food and Agriculture’s Expanded Food and Nutrition Education Program*.

Table 5. Description of COPE experiential and communal activities	
Communal cooking	Advance meal preparation to promote home cooking using foods from WIC/food bank, and decrease reliance on fast-food. Gatherings are lead by [name] (Site Culinary Program Coordinator) and take place in the Wellness Homes operated by our partner (Resources & Environment section).
Community gardening	Mariposa master gardeners teach parents/children gardening techniques (planting, growing and harvesting fruits and vegetables). Gardens are located on Wellness Homes’ grounds. Families tend local gardens with other families.
Food management	Classes to improve food resource management practices such as purchasing, selecting, or otherwise obtaining; preparing; and storing foods to increase sustained availability of healthy foods throughout the month. This material is delivered in local grocery stores and markets.
Mobile food demos	Food demonstrations hosted in neighborhood farmers markets to provide convenient and accessible cooking and food preparation demonstrations using fresh products from local farmers markets.

**C.5. Measurements.** HVP *Assessment Workers* (registered nurses who can draw blood) who enroll families into standard HVP services, have been trained to screen and recruit eligible families for the proposed project. They will administer the assessments (English or Spanish; **Table 6**) in the families’ homes or at the HVP clinic (as needed) at baseline/enrollment, and after 6mo and 12mo of services. *Home visitors* will be trained to gather interim (objective) weight measurements for the purpose of generating more frequent data points, triangulated with the assessment workers’ measurements.

**Medical and family history.** A thorough family history and physical examination will be conducted at baseline. We will collect demographic data, including socioeconomic status (education, income, eligibility for SNAP).

**Infant growth & waist trajectories.** Weight will be measured on a digital scale (Tanita) accurate to the nearest 5g. Length will be measured to the nearest 0.1 cm using an infanto-meter using the standardized WHO approach,

Table 6. Assessment time points (month of intervention) and key measures							
	Baseline	3	6	9	12	15	18
COVARIATES							
Demographics, household composition, medical history, post-partum depression, activity readiness	X						
MOTHERS							
Weight/height, waist circumference	X	X	X	X	X	X	X
Blood and vitals	X						X
24h diet & activity recall	X		X				X
Feeding and food insecurity	X		X				X
Social support and networks	X		X				X
Home environment	X		X				X
INFANTS							
Weight/length, waist circumference	X	X	X	X	X	X	X
Blood (finger prick)	X						X
24h diet & activity recall (from mother)	X		X				X

including use of staff training modules. Weight and length will be used to calculate weight-for-length and weight-for-age z-scores (WHO Standards), as recommended by the CDC for children <24 mos. Infant growth rates will be examined as the change in WLZ from baseline to follow up (12mo) Waist circumference will be measured at the umbilicus (nearest 1-mm) using a non-stretch measuring tape.

**Infant diet & activity.** To fully capture *infants' diet* (e.g., breastfeeding, use of formula, fruits/vegetables, fat/sugar intake), we will use multiple tools. *Diet recall.* Mothers will be interviewed about their *infants' intake* of fruits, vegetables, friend foods, and sugared beverages. Mothers will complete items from the *Diet and Behavior Questionnaire (DBQ)* of the National Health and Nutrition Examination Survey to capture breastfeeding/feeding history and introduction to

formula and solid foods. *Infants' activity.* Because of validity issues related to accelerometry in infants/young children, we opted to capture time engaged in sedentary activities and structured/unstructured physical activity. Mothers will report their child's activities (e.g., tummy time,)

**Infants and maternal biomarkers for metabolic risks.** Blood will be drawn at the Antelope Valley Partners for Health office by Assessment workers with phlebotomy certification, at baseline for mothers only. *Mothers:* Blood will be drawn by Assessment Workers who will make a maximum of 3 attempts to draw the blood during the first visit. If the first attempt is not successful, mothers will be invited to return on another day for a second (and final) attempt. Plasma will be stored at -70°C for analysis. Biomarkers of type 2 diabetes risk, lipids, and inflammatory markers. CRP will be measured using the Millipore Multiple assay kit at the USC DORI Core Laboratory. Lipids will be assayed using Vitros Colorimetric assays (Johnson & Johnson Clinical Dinostics Rochester, NY) for cholesterol, triglycerides and HDL-cholesterol. Sitting blood pressure (mothers) using auscultation and heart rate will be measured on the right arm after a 5-minute rest. Three readings of blood pressure and heart rate will be obtained and the average of the last two last will be recorded.

**Maternal weight & waist circumference.** Weight and height will be measured by Assessment Workers in participants' homes using an electronic scale (Model BWB-800S, Tanita, Portage, MI) and stadiometer (Model PE-AIM-101, Perspective Enterprises) according to standard procedures. Subjects will remove shoes, belts, and heavy outerwear and empty pockets. We will measure height in duplicate and if measurements are not within 0.5 cm, we will obtain a third measurement. The mean of all measurements will be used to calculate BMI. Waist circumference will be measured at the umbilicus to the nearest 1 mm using a non-stretch measuring tape. Maternal obesity prior to pregnancy will be derived from pregravid BMI (recall during pregnancy at recruitment). Gestational weight gain will be defined as the last weight obtained before delivery minus the pregravid recalled weight or the weight recorded at the first prenatal visit during the first trimester using electronic medical record data.

**Maternal diet & activity.** Mothers' dietary intake and activities will be assessed using several items from NHANES (2017), including intake of fruits and vegetables, fried foods, and sugary-sweetened beverages, and time mothers engage in moderate physical activity.

**Maternal social networks & support.** Using egocentric social network methods and EgoWeb software (<http://www.rand.org/methods/egoweb.html>, developed with PI [name]), we will assess the characteristics of the social actors (people, organizations) and relationships that surround mothers. Using standard name generator items, participants are asked to identify 20 important adults in their lives, and then report on the attributes of each person (demographics, health attributes/behaviors) and types of relationships they share. Relationship characteristics of interest include how they know the person (e.g., family, friend from a community program, etc.), frequency of interaction, and provision of support for health behaviors (e.g., encouragement for or co-engagement in specific behaviors). *Social Support measures from the PROMIS database* will be used to assess emotional and instrumental support, and social isolation. Egocentric network data is used to compute network composition variables (e.g., proportions of family/friends in the network), and variables that represent

important network structures (e.g., sparse or dense support). Respondents will also be asked about health-related relationships (e.g., information seeking, support) they have with community organizations. Social network analysis (SNA) will be used to compute summary statistics for each mother's network, such as the proportion of network members that engage in regular exercise or that provide health-relevant support, and the density of supportive relationships.

**Maternal food insecurity.** The U.S. Adult Food Security Survey Module is an 18-item, three-stage design with screeners. Each stage consists of characteristic conditions and experiences of food insufficiency to meet the basic needs of household members, and of the behavioral responses of household members to these conditions. We will test if scores mediate the effect of COPE on infants' outcomes, as energy intake and weight are related to food insecurity.

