**C. APPROACH**

This research is designed to integrate and leverage our team’s expertise (**Table 1**), as detailed in the *Personnel Justification* section, *Multiple PI Plan*, and *Biosketches*.

**C.1. Design overview.** **Table 2** depicts the logic model of the proposed study, and demonstrates its scientific rigor. Healthy Families America home visitors (see *Intervention arms* below for their qualifications) will be randomized to deliver the HVP curriculum with or without COPE for 12 months (standard HVP duration). Mothers/infants will be recruited and enrolled on a rolling basis over 24 months (study months 6-30), and

matched to a home visitor based on race, ethnicity and language preferences. Assessment of mothers and infants will be conducted by *assessment workers* (who are blind to study assignment) at enrollment, and after receiving 6 and 12 months of services. \*\*

	[name]	[name]	HFA	[name]	[name]	[name]	[name]
Infants and early childhood obesity/nutrition	x		x	x	x		
Home visitation services			x				x
Family-based behavioral obesity interventions	x						
Underserved, racial/ethnic populations and culturally/linguistically tailored interventions			x	x	x		x
Multilevel interventions for behavior change	x	x					
Social network measurement and analysis		x					
Longitudinal modeling of multilevel data		x				x	
Cost analyses of childhood prevention efforts							x

The assessment of participants after they ceased to receive services for a given period of time (i.e., “true” follow-up) is impossible because of the ongoing nature of HVP services. We believe that asking home visitors to withhold the delivery of the COPE material to allow for a “no COPE” period would be unrealistic in terms of potential contamination, and also create an uncomfortable situation for families and HVP staff.

SITUATION: More than 40% low-income children enrolled in federally funded programs are overweight or obese by age 5. Obesity efforts have limited impact among underserved, low-income children, at risk for obesity.		
INPUTS	OUTPUTS	OUTCOMES

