
**C.3. Participants.** Participants will be low-income mothers/infants (6mo at enrollment) *who are already receiving services from our HVP partner (Figure 6)*. Thus, study enrollment does not require that we recruit more families than our HVP partner is already enrolling. Mothers are enrolled in HVP services through outreach and screening pre-partum, in English or Spanish, at community health centers and hospitals. In order to be eligible mothers must meet a number of (but not all) risk criteria (e.g., low-income, housing instability). Enrolled mothers are matched to a home visitor (nurse) based on culture and language. **Recruitment.** Assessment workers (distinct from home visitors delivering services) who enroll families into services will introduce the study to mothers and obtain written consent. They will clarify with mothers that their refusal to participate in the study will not affect their receipt of any other services provided by the HVP. In our experience, families feel comfortable refusing if they are not willing to participate. Mothers/infants will be ineligible if they have any of the following conditions: eating disorders (e.g., bulimia nervosa), schizophrenia, and obesity-related syndrome (e.g., Prader Willi). Participants enrolled in a weight-loss program will be ineligible. Based on our pilot work, we expect to recruit 70% Hispanic/Latino, 13% African American, 8% White, 5% American Indian/Alaskan, 4% mixed race. **Retention.** We have learned a great deal about retention through our pilot work. For instance, most attrition from HVP services occurs in the first six months of services. Therefore, to maximize retention, mothers will be invited to participate in the study *after six months of home visits*. The unique relationship between home visitors and mothers facilitates subsequent retention, as many of these mothers are socially isolated and home visitors are important confidants and supports. We will use multiple strategies that are effective for high-risk populations to further retain the study sample: (1) gift cards of \$25 at each data collection, with all incentives paid after each assessment; (2) frequent contacts to maintain engagement and foster open communication; (3) quarterly newsletters to update subjects about study activities; (4) acknowledging birthdays and milestones; (5) reminder phone calls the day before the weekly visits and assessment sessions. **Randomization.** Randomization will be at the level of home visitors, who deliver the HVP (cluster randomization). Home visitors who serve mothers that are participating in the proposed study will be randomly assigned to deliver either HVP only or HVP+COPE. Potential concerns with randomizing by home visitors are feasibly addressed in this study. First, the likelihood of

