**Aim 1 (maternal/infant outcomes).** Change in weight-related outcomes over the 2-year implementation is the primary outcome comparison. We will use multilevel regression models adjusting for clustering effect of home visitors to compare differences in the main outcomes across time by intervention arm. Regression model can be treated as a special case of path model without mediators. These regression models will include all participants, who have at least 2 measurements, regardless of when the measurements are taken, increasing the follow-up of study participants and statistical power. Specific measures relevant to Aim 1 are maternal and children weight-related measures. These models will allow the evaluation of intervention effects on, for example, child growth trajectory and activity, and mother BMI, metabolic, and behavior outcomes. Investigation of the main effects of COPE on outcomes will be conducted at each follow-up. Baseline outcome measures will be treated as covariates to control for potential

baseline differences. Effects of COPE will be evaluated first at each follow-up assessment point. Longitudinal analyses with all follow-up points (6 and 12 months) will then be conducted to examine profiles across time to investigate the effects of program conditions on trends of outcome measures.

**Aim 2 (maternal transmission).** To estimate the mediational effects of maternal transmission, multilevel path models will be developed and evaluated per our hypotheses. The model specification will be guided by our conceptual model treating Intervention program as the distal variables along with demographic variables to affect mother's weight, diet and behavior as mediators, which in turn may influence infants' outcome. While the intervention program will be at the Level-2 unit, all other variables included in the multilevel path models will be Level-1 variables obtained from mothers and children. Using breastfeeding and maternal diet on infants' weight trajectories as an example, the mediation mechanism of maternal transmission can be expressed by the process: COPE → breastfeeding \* maternal diet → weight. The path model will allow the test of both the direct effect of COPE on infant weight trajectory and its indirect effect on through breastfeeding and maternal diet.

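### No rule keeps interim weights taken by unblinded home visitors out of the primary Aim 1 weight comparison

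*Combined protocol and SAP*

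**What the plan says.** **Who is randomised.** C.3 (Randomization): "Home visitors who serve mothers that are participating in the proposed study will be randomly assigned to deliver either HVP only or HVP+COPE". C.2 and C.3 add that visitors are trained and supervised separately by arm.

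**Who is blind.** C.1 attaches blinding to the assessment workers and their scheduled visits: "who are blind to study assignment) at enrollment, and after receiving 6 and 12 months of services" (the bracket is the source's).

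**Who weighs in between.** C.5 states that home visitors "will be trained to gather interim (objective) weight measurements for the purpose of generating more frequent data points". The only safeguard is in the same sentence: "more frequent data points, triangulated with the assessment workers", meaning those workers' measurements. It gives no tolerance, no order of precedence and no rule for disagreement.

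**When.** Table 6 marks maternal weight/height and waist, and infant "Weight/length, waist circumference", at baseline and months 3, 6, 9, 12, 15 and 18. The fuller battery (recalls, feeding, networks) appears at baseline, 6 and 18. Table 7 also lists 6- and 18-month assessments, whereas the text of C.1, C.5 and C.6 gives 6 and 12 months.

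**What is primary.** C.6, Aim 1: "Change in weight-related outcomes over the 2-year implementation is the primary outcome comparison". On the data used: "These regression models will include all participants, who have at least 2 measurements, regardless of when the measurements are taken". The reason given is longer follow-up and more power.

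**Text pointing the other way.** C.6 (General strategy) describes three waves: baseline, 6 and 12 months. Aim 1 names 6 and 12 months as the follow-up points of the longitudinal analysis. C.5 defines infant growth as change in weight-for-length z-score (WLZ) from baseline to 12 months, and assigns maternal weight and height to the assessment workers.

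**The concern.** Interim weights are collected to create extra data points, and the Aim 1 models are justified by the follow-up and power that extra measurements bring. Read together, the two passages let visitor weights into the primary comparison.

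In those readings, the measurer's knowledge of arm coincides with arm. Every interim weight in the HVP+COPE arm comes from a COPE-trained visitor, and every one in the control arm from a control visitor. A shared difference in clothing or diaper practice, time of weighing, repeat weighing or selective recording would load onto the treatment coefficient.

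The model does not repair this. Arm is constant within visitor, so a visitor random effect absorbs variation between visitors within an arm but not an offset common to all visitors in one arm. Adjusting for baseline does not help either, because assessment workers take the baseline reading and it does not carry the offset.

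Early loss adds to the problem. A dyad lost after month 3 would meet the two-measurement rule on a baseline reading plus one unblinded weight. The plan expects to lose between 25% of 300 = 75 dyads and 300 − 200 = 100 dyads.

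**Working it through.** **1. The plan's own figure.** The Power Analysis gives a detectable Cohen's f of .17 to .20 with N = 200, two-sided alpha .05 and inflation factors (DE) of 1.4 to 1.8. It states neither the number of occasions m, nor the within-person correlation rho, nor the power behind that figure. I used the repeated-measures between-groups F test with noncentrality f²·(200/DE)·m / [1 + (m − 1)rho], degrees of freedom 1 and (200/DE) − 2, and 80% power (assumed):

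| Occasions m | rho (assumed) | f at DE 1.4 | f at DE 1.8 |
|---|---|---|---|
| 1 | – | .236 | .268 |
| 3 (blinded waves) | .3 | .172 | .196 |
| 3 | .5 | .193 | .219 |
| 7 (all of Table 6) | .3 | .149 | .170 |
| 7 | .4 | .164 | .187 |
| 7 | .5 | .178 | .203 |

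Three waves with rho = .3 match the stated range, but seven occasions with rho between .4 and .5 come close too. The figure is therefore not uniquely reproducible, and it does not reveal which readings the authors meant to use.

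**2. Exposure.** Follow-up weights with no blinded worker assigned:
- 12-month schedule, workers at 6 and 12: months 3 and 9, so 2 of 4.
- Table 6 to month 18, workers at 6 and 18: months 3, 9, 12 and 15, so 4 of 6.
- Table 6 to month 18, workers at 6, 12 and 18: months 3, 9 and 15, so 3 of 6.

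**3. Bias for a constant offset d.** Here d is the assumed systematic difference between the two arms' visitor readings; the documents give no value. I assume complete data.

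Mean of follow-ups: bias = d × (visitor readings / all follow-up readings).

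Least-squares slope, expressed as total change: bias = d × T × Σ(t − t̄ at visitor months) / Σ(t − t̄)².
- 0–12 months: deviations −6, −3, 0, 3, 6; sum of squares 90. Visitors at 3 and 9: −3 + 3 = 0.
- 0–18 months: deviations −9 to 9 in steps of 3; sum of squares 252. Visitors at 3, 9, 12 and 15: −6 + 0 + 3 + 6 = 3, and 18 × 3/252 = 0.214.
- 0–18 months, visitors at 3, 9 and 15: −6 + 0 + 6 = 0.

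| Visitor months | Mean contrast | Slope contrast |
|---|---|---|
| 3, 9 (0–12) | 2/4 = 0.5d | 0 |
| 3, 9, 15 (0–18) | 3/6 = 0.5d | 0 |
| 3, 9, 12, 15 (0–18) | 4/6 = 0.67d | 0.21d |

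**4. Illustrative type I error for the mean contrast.** SE = √{[1 + (m − 1)rho]/m} × 2/√(200/DE), in SD units, with m the number of follow-ups. Example: m = 4, rho = .5, DE = 1.4 gives √(2.5/4) × 2/√142.9 = 0.132. With d = 0.2 SD the bias is 0.10 SD and the two-sided error is .118 instead of .05. Ranges over DE 1.4 to 1.8 and rho .5 to .7 (normal approximation):

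| Assumed d (SD) | 2 of 4 readings | 4 of 6 readings |
|---|---|---|
| 0.1 | .06–.07 | .07–.08 |
| 0.2 | .09–.12 | .13–.18 |
| 0.3 | .15–.21 | .23–.35 |

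**The case against.** The strongest reply is that the Aim 1 sentence defines which participants are analysed, not which readings form the outcome, while four other statements name the blinded waves or a baseline-to-12-month change. On that reading the per-visit and 12-month analyses use assessment-worker values and the bias is zero. This largely stands. A reader might infer that the plan declares that every measurement enters the models; it does not. What remains is that no sentence excludes visitor weights, and the stated reason for collecting them matches the stated reason for the inclusion rule. Two analysts could build different primary datasets in good faith.

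Second, a digital scale leaves limited room for rater influence, and random noise in both arms does not bias the contrast. That is also true: only a systematic arm difference matters. C.5 sets clothing rules for weighing mothers but none for infants, so room for such a difference remains.

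Third, a reader might extend the point to length and waist. The documents give visitors weight only and do not say who measures length or waist at the interim months. WLZ needs length, so a visitor's weight alone cannot produce an interim WLZ. Exposure is clearest for weight and weight-for-age. For maternal BMI it is only possible, since C.5 assigns maternal weight to assessment workers while Table 6 lists interim maternal weights without naming a measurer.

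**Conclusion.** The concern holds as an unreconciled gap. As written, unblinded visitor weights can enter the primary weight models, and nothing in the modelling would remove a systematic arm difference in them. The direction and size of any such difference cannot be derived from the documents. Conditional on an assumed constant offset d and complete data, the bias is 0.5d to 0.67d for a mean-of-follow-ups contrast and 0 to 0.21d for a linear slope. The type I figures are illustrations, not estimates.

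Two larger readings are not supported. Placing visitors at months 3, 9, 15 and 18 gives a slope bias of 18 × 9/252 = 0.64d, but it makes visitors the measurers at month 18, which Table 6 shows as a full assessment with blood draws, a task C.5 gives to assessment workers. A reader might also express the bias as a share of the pilot effect of 0.4. That effect is for weight velocity, whereas the averaged bias is in weight level, so the ratio has no clear meaning.

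**What to change.** In C.6, Aim 1, state that the primary weight analysis uses only baseline and follow-up readings taken by the blinded assessment workers. Reword the any-time inclusion sentence to agree, and reconcile it with Table 6 and with the 12-month, 18-month and 2-year time frames. Add a field recording the measurer's role for every reading; this must be captured at collection, as it may not be recoverable later. State who measures length and waist at the interim months. Use visitor weights in a labelled sensitivity analysis of the trajectory and in an agreement check against assessment-worker readings by arm, and let that check define what triangulation means.

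The cost is a few sentences, one form field and fewer repeated weights in the main model. Moving from seven occasions to three raises the detectable f from .149–.170 to .172–.196 at rho = .3, which still matches the stated .17 to .20. At rho = .5 it goes from .178–.203 to .193–.219, slightly above the stated range. Both assume 80% power.
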